## Statistical Analysis Plan

### **8.3.11. Association between ORR and ADA Status**

Exploratory analyses will assess whether there is a relationship between anti-drug antibody positivity for AZD9150 and MEDI4736 and objective response. Patients will be defined as being ADA positive to a particular drug if the patient has at least 1 post-treatment positive ADA test for that drug. The odds ratio for having an objective response in the ADA-positive groups compared to having an objective response in the ADA-negative groups will be calculated for both Part A and Part B.

Due to the small number of patients in each treatment arm in Part A, patients who received different doses of within a treatment arm might be combined when assessing the relation between ADA status and objective response. The odds ratio for patients having an objective response in the ADA-positive group will be compared to the patients having an objective response in the ADA-negative group. An 80% CI will be provided for the odds ratio using a chi-square assessment, where zero cells are adjusted with a value of 0.5.

In Part B, separate odds ratios will be calculated for each of the relevant treatment arms and anti-PD-(L)1 status combinations. Again, 80% CIs will be provided for each odds ratio estimate, where zero cells are adjusted with a value of 0.5.

For Part B, a logistic regression model may be used to estimate the probability of having an objective response using treatment group and anti-PD-(L)1 status as factors and the maximum post-treatment antibody titer level as a continuous variable.

### **8.3.12. Association between ORR and Human Papilloma Virus**

PD-1/PD-L1 expression has been proposed to play a role in the immune resistance of human papillomavirus-associated squamous cell carcinomas of the head and neck (SCCHN). Consequently, blocking the PD-1/PD-L1 pathway may aid the effectiveness of immunotherapy in the treatment of HPV-associated SCCHN carcinomas. In Part B, the association between HPV-positivity and objective response will be assessed by comparing the odds for patients having an objective response in the HPV-positive group to the odds for patients having an objective response in the HPV-negative group. An 80% CI will be provided for the odds ratio using a chi-square assessment, where zero cells are adjusted with a value of 0.5.

## Statistical Analysis Plan

### 9. ANALYSIS OF PHARMACOKINETICS

The PK population will be used in all PK analyses. The PK parameters identified in Section 4.4 will, where possible, be determined from the plasma concentrations of AZD9150, AZD5069, treme, and MEDI4736, using non-compartmental procedures performed by Covance on behalf of AstraZeneca.

Actual blood sampling times post-dosing will be used in calculation of PK parameters. Concentrations are used as supplied by the analytical laboratory for PK analysis. The units of concentration and resulting PK parameters, with the amount or concentration in the unit, will be presented as they are received from the analytical laboratory.

#### **Presentation of Pharmacokinetic Concentration and Parameter Data**

Plasma concentrations of AZD9150, AZD5069, treme, MEDI4736 and any significant metabolites will be summarized by nominal time point and visit for each treatment group.

The PK data for AZD9150, MEDI4736, treme and AZD5069 will also be displayed graphically. Displays will include individual patient plasma concentration versus time profiles, on both the linear and log-scales. Additionally, the  $\text{gmean} \pm \text{StD}$  concentration versus time profiles will be summarized by treatment group. These plots will include the extensive concentration data collected at the specified study times for AZD9150, AZD5069, treme, and MEDI4736 according to the schedule of study assessments.

If data permits, for both Part A and Part B, the  $\text{gmean} \pm \text{StD}$  concentration versus time profiles for the AZD9150 groups will be displayed graphically by anti-AZD9150 antibody status (i.e., positive/negative).

All plasma concentration data for AZD9150, AZD5069, MEDI4736, treme and any active metabolites will be listed. All PK parameters will be listed.

## Statistical Analysis Plan

### 10. ANALYSIS OF PHARMACODYNAMICS

The Pharmacodynamics population will be used in all pharmacodynamic analyses. No inferential analyses will be performed on the pharmacodynamic endpoints, which will be summarized using descriptive statistics.

#### 10.1.1. STAT3 Knockdown by AZD9150

These results will be reported separately and will not be part of the CSR.

#### 10.1.2. Soluble Programmed Cell Death-Ligand 1 (sPD-L1)

The soluble programmed cell death-ligand 1 (sPD-L1) assay uses a quantitative competitive electrochemoluminescence (ECL) immunoassay format to measure the concentration of MEDI4736-free sPD-L1 protein (soluble target not bound to drug) in human serum with a lower limit of quantitation (LLoQ) of 15.6 pg/mL.

In both the dose-escalation (except safety cohorts A3, A4, and A6) Part A and dose-expansion Part B (B1-B6) of the study, blood samples (3.5 mL) for evaluation of circulating sPD L1 protein (MEDI4736) will be collected from patients on Day 1 of Cycle 1; on Day 15 of Cycle 2; and on Day 1 of all subsequent even-numbered cycles. On Day 1 of Cycle 1 and on Day 1 of Cycle 8, in addition to the predose sample, a sample will also be obtained at the end of the MEDI4736 infusion. For patients who discontinue MEDI4736, a sample will be drawn 90 days after their last dose of MEDI4736 coinciding with an IM (ADA) sample. For patients in Arm B1, B2, and B4 sPDL1 samples will not be collected after the first 20 patients. The sPDL1 samples will also not be collected for Arms B7 and B8. Summary tables will report descriptive statistics for sPD-L1 levels and the change from baseline by visit for each MEDI4736 treatment group. A line plot with error bars presenting the median sPD-L1 level by visit and treatment group will be provided. All sPD-L1 data will be listed.

#### 10.1.3. Circulating Myeloid-Derived Suppressor Cells (MDSCs)

For all patients, blood samples for MDSC (5 mL), will be collected pre-dose at the specified time points to assess the treatment effect on circulating MDSCs: At screening, Day -7 of the lead-in period, Day 1 of Cycles 1, 2, 3, 5, and at the EOT visit.

For patients in Arm B1, B2, and B4 MDSC samples will not be collected after the first 20 patients. MDSC samples will also not be collected for Arms B7 and B8. Summary tables will report descriptive statistics including median results for circulating MDSC levels and the change from baseline by visit for each AZD5069 treatment group. A line plot with

## Statistical Analysis Plan

error bars for the median circulating MDSC level by study day and treatment group will be provided. All circulating MDSC data will be listed.

For each sample per patient, there are 9 reportable parameters at most. For some samples, the parameters with “CD33” have this or similar lab error comments, “Abnormal expression identified, raw data available upon request”. AstraZeneca analyzed the raw data, identified the basis of the lab error, and found the following three parameters of these samples were affected by this lab error:

1. Lin-HLA-DR-/loCD33+CD11b+ %(Lin-) %
2. Lin-CD15+HLA-DR-/loCD33+CD11b+ %(CD15+) %
3. Lin-CD15+HLA-DR-/loCD33+CD11b+ %(total) %

Thus, the above reportable parameters for subjects with lab error at the relevant visits will be excluded from summary plots or figures. All other verifiable visits for such subjects will be included.

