To assess tumor cell pharmacodynamics (STAT3 knockdown)	Pharmacodynamics of AZD9150 (STAT3 knockdown) in tumor tissue
To assess baseline circulating MDSCs and effect of treatment on circulating MDSCs (will not be evaluated for Arms B1, B2, and B4 post the first 20 patients and for Arms B7 and B8)	Circulating MDSCs
To evaluate baseline tumor PD-L1 expression for potential correlation with drug activity or the ability to prospectively identify patients likely to respond to treatment	Tumor PD-L1 expression

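### The exclusion of lab-error MDSC values in SAP 10.1.3 names plots and figures but not the summary tables, and no baseline rule covers an affected sample

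*SAP*

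**What the plan says.** Protocol 2.2 makes MDSCs a Part B secondary objective: "To assess baseline circulating MDSCs and effect of treatment on circulating MDSCs". SAP 4.4 names them as the pharmacodynamic endpoint for AZD5069.

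SAP 10.1.3 plans three outputs:

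- Tables: "Summary tables will report descriptive statistics including median results for circulating MDSC levels and the change from baseline by visit for each AZD5069 treatment group".
- Plot: the median level by study day and treatment group, as lines.
- A listing: "All circulating MDSC data will be listed".

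The section then describes the laboratory problem. "For each sample per patient, there are 9 reportable parameters at most". For some samples the CD33 parameters carried an error comment. The sponsor went back to the raw data, identified the cause, and "found the following three parameters of these samples were affected by this lab error". The rule that follows is: "Thus, the above reportable parameters for subjects with lab error at the relevant visits will be excluded from summary plots or figures". Its companion sentence is: "All other verifiable visits for such subjects will be included".

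**The concern.** The sponsor has already judged these values to be wrong, so the only open question is which outputs they leave. The exclusion sentence names plots and figures, which are one kind of output, and omits tables. The tables hold the numerical results for this endpoint. In SAP 10.1.3 the only planned graphic shows the median level, so change from baseline, the quantity that speaks to a treatment effect, is planned in tables alone and lies wholly outside the stated exclusion.

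A programmer who follows the text would drop the values from the line plot and keep them in the table. The median for the same parameter, visit and group could then differ between the two, and the table would carry results known to be invalid.

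The second gap concerns baseline. The rule acts on the visit with the error. It says nothing about quantities derived from that visit's value and reported at other visits.

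**Working it through.** There is no planned figure to reproduce. The check sets the exclusion sentence beside every SAP rule that could remove an erroneous value from a table.

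**1. Does another rule keep the values out of the tables?**

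- SAP 5, Pharmacodynamics set: defined by patient, with exclusion only for important protocol deviations. It has no rule by sample or parameter.
- SAP 7.2: laboratory issues are one category of deviation, but important deviations remove whole patients from analysis sets, and the section is not linked to this error.
- SAP 6.3: no imputation of missing data, and no rule that sets an erroneous value to missing.
- SAP 6.1: continuous pharmacodynamic variables are summarised by n, mean, standard deviation, median, minimum and maximum, with no validity condition.
- Protocol 8.10: summaries of change and percent change from baseline for pharmacodynamic variables, with no exclusion.

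None of these closes the gap.

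**2. What happens if the baseline sample is affected?**

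- SAP 6.2 takes baseline, unless otherwise specified, as the last non-missing observation before study treatment starts in Cycle 1. It does not ask that the observation be valid.
- SAP 10.1.3 schedules pre-dose MDSC samples at screening, Day -7, Day 1 of Cycles 1, 2, 3 and 5, and end of treatment. The usual baseline is therefore Cycle 1 Day 1 pre-dose.
- If that sample carries the error and is not set to missing, it remains the baseline. It enters the change at Cycles 2, 3 and 5 and at end of treatment, up to 4 changes per affected parameter, even where those later samples are sound.

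**3. Would setting the value to missing settle the matter?**

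Not by itself. SAP 6.2 would then fall back to Day -7 pre-dose or to screening. AZD5069 starts on Day -7 (Protocol 7.2.2), so those samples precede the drug, whereas Cycle 1 Day 1 follows a week of lead-in dosing. An unstated fallback would mix pre-drug and on-drug baselines in one table.

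**4. Size**

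- Parameters: 3 of at most 9.
- Affected samples, patients and baselines: not given, so the shift in any tabulated statistic cannot be computed.
- Illustration only, for one affected baseline. MDSC sampling in B2 and B4 stops after the first 20 patients (read here as 20 per arm): 1/20 = 5%. B6 plans 12 patients: 1/12 = 8.3%. Both assume a full sample; the share rises as patients drop out.

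**The case against.** The strongest reply is that the sentence is a slip. Plots and figures are the same thing, so the author may have meant tables or figures. The companion sentence, "All other verifiable visits for such subjects will be included", is not limited to graphics and can be read to imply that unverifiable results leave every summary. The table shells are in separate documents (SAP 15) and may carry the exclusion. These readings are possible, but none changes the scope that the SAP states, and shells that cannot be seen cannot be relied on. A slip in an exclusion rule still needs correcting.

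The consequence is also modest. SAP 10 plans no inferential analysis of pharmacodynamic endpoints. The Part B stopping and expansion rules use objective response. The error is disclosed, the parameters are named and all data are listed. Medians resist a few bad values, although the mean, standard deviation, minimum and maximum also planned in SAP 6.1 do not. All this limits the severity and stands.

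A reader might infer three stronger things that the documents do not support:

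- That invalid baselines are known to be in the tables. No text says that any baseline sample was affected.
- That the SAP expressly keeps the erroneous values in the tables. It is silent, and their retention follows from the limited scope of the exclusion.
- That B1 belongs in the count because its MDSC sampling also stops at 20 patients. B1 receives AZD9150, and the tables are by AZD5069 group.

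**Conclusion.** The point holds as a gap in wording. Followed as written, SAP 10.1.3 lets values that the sponsor has found to be wrong into the tabulated levels and changes of a Part B secondary endpoint, and no other rule in the SAP takes them out. The baseline problem is conditional on at least one affected baseline sample. The damage is limited to descriptive summaries of three parameters in the AZD5069 groups and has no bearing on the primary endpoint or on any decision rule. Its size depends on a count of affected samples that the documents do not give. The SAP should be corrected because the remedy is specific and nearly free.

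**What to change.** In SAP 10.1.3:

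1. Extend the exclusion, for example: *excluded from all summary tables, plots and figures, including any change from baseline derived from an affected value*.
2. Keep the affected values in the listing with a flag.
3. State one baseline rule for the affected parameters. Two choices are defensible. Either change from baseline is set to missing at all visits when the baseline value is affected, or a named earlier valid sample taken before Cycle 1 replaces it. The first loses some valid later data. The second keeps them, but the SAP should note that screening and Day -7 pre-dose samples precede lead-in dosing and Cycle 1 Day 1 does not.

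It would also help to report the number of affected samples and baselines by group.

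The cost is a few sentences in the SAP, one flag in the programming, and possibly fewer observations in the MDSC tables. Neither the design nor data collection changes.

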### 10.1.4. Tumour PD-L1

Summary tables will report descriptive statistics for tumour PD-L1 levels at baseline. All post-baseline tumour PD-L1 data will be reported separately and will not be part of the CSR.

## Statistical Analysis Plan

### 11. SAFETY

No inferential testing will be performed on safety data, which will be summarized using descriptive statistics.

Part A focuses primarily on determination of the MTD for the AZD9150/MEDI4736 and the AZD5069/MEDI4736 drug combinations in patients who have completed the DLT evaluation. Section 11.1 discusses the safety assessments unique to identifying the MTD in dose-escalation Part A.

The remaining safety endpoints—treatment exposure, AEs, SAEs, laboratory evaluations, vital signs, and physical examinations, ADAs—are common to both Part A and Part B. These common safety endpoints will be analyzed using the same methods, which are discussed starting in Section 11.2 of this SAP.

For patients who have a dose modification, all AEs (due to drug or otherwise) will be assigned to the associated initial dose combination/dose level.

Safety data will be presented graphically as deemed appropriate. This may include, but is not restricted to, presentation of parameters against time or shift plots. Appropriate scatter plots will also be considered to investigate trends in parameters compared to baseline.

#### 11.1. DOSE-ESCALATION AND SAFETY COHORTS – PART A

##### 11.1.1. Starting Dose and Dose-escalation Scheme

AZD9150 will be administered at a starting dose of 2 mg/kg IBW. Additional dose levels up to 3 mg/kg IBW may be evaluated.

AZD5069 will be administered at a starting dose of 40 mg PO BID (ie, daily dose of 80 mg). Additional dose levels up to 120 mg BID (for a maximum total daily dose of 240 mg) may be evaluated.

MEDI4736 will be administered at a dose of 20 mg/kg Q4W. A dose of 10 mg/kg Q4W might be investigated as an additional dose level.

Combination treatment in treatment arm A1 (AZD9150/MEDI4736) will start with doses of AZD9150 2 mg/kg IBW and MEDI4736 20 mg/kg; combination treatment in treatment arm A2 (AZD5069/MEDI4736) will start with doses of AZD5069 40 mg BID and MEDI4736 20 mg/kg.

## Statistical Analysis Plan

A CRM-based approach will be used to identify the set of AZD9150/MEDI4736 and AZD5069/MEDI4736 dose combinations where the incidence of DLT is no larger than 33%. In each cohort, up to 3 patients will be initially assessed. Dose escalation to the next higher dose level for the next cohort group of 3 patients will occur if all 3 patients in the initial cohort complete Cycle 1 without DLT. Following the first DLT, the CRM model will be run and the output made available to the SRC to guide further dosing decisions (see Section 11.1.2 for details).

Tolerated combination doses will be defined as combinations for which the DLT incidence is no larger than 33%. Prior to the occurrence of the first DLT, a cohort will consist of 3 patients; following the first DLT, cohorts will require a minimum of 6 patients before dose escalation may occur. In all cohorts, the sample size refers to patients who are evaluable for dose escalation; patients who are nonevaluable for dose escalation will be replaced (See Section 5.4.3 of the study protocol for the criteria to be deemed evaluable for dose-escalation purposes).

Dose escalation will be defined as an increase in the dose of at least 1 of the drugs without decreasing the dose of the other.

Dose escalation for the 2 combination treatments (ie, AZD9150/MEDI4736 and AZD5069/MEDI4736) will advance independent of each other. In addition to determining DLT in the DLT evaluation period, the SRC will critically review all available data pertaining to safety, tolerability, and IM as well as PK, pharmacodynamic, and antitumour activity before deciding on the next dose levels to be explored. Dose escalation in each arm will be considered completed once 1 of the following criteria is met:

- The MTD (for definition of MTD see Section 5.3.3 of the study protocol) for the 2 agents in combination have been identified
- The SRC has recommended doses for the 2 agents in combination to be further explored in the dose-expansion Part B
- The maximum doses of the 2 agents in combination have been reached (ie, AZD9150 3 mg/kg IBW, AZD5069 120 mg BID [for a maximum total daily dose of 240 mg], and MEDI4736 20 mg/kg)

## Statistical Analysis Plan

### 11.1.2. Use of the CRM to Select Recommended Doses to the SRC

The CRM computations that are needed to generate the dose-escalation recommendations will be made using the R package, *dfcrm* (Dose Finding for the Continual Reassessment Method). Documentation regarding the *dfcrm* package can be found in Cheung (2011) and online at <http://www.r-project.org/>

Because there are only a few possible outcomes for the number of DLTs that can be observed in a cohort, it is possible to provide the model estimated MTD for all possible outcomes of DLTs within a cohort in advance of an SRC meeting. Similarly, the posterior variances can be calculated for each possible outcome, allowing us to define whether the CRM will recommend stopping or proceeding to dosing of the next cohort. These recommendations can be summarized in a “playbook”, which can be provided to the SRC in advance of each meeting. The playbook will be generated using only data from evaluable patients as defined in the protocol (Section 6.2).

Appendix 1 shows the playbook contents for the first cohort of 3 patients treated at the starting doses for the 2 combination drugs. For each of the possible DLT outcomes for the first cohort (i.e., 0 DLTs/3 patients, 1 DLT/3 patients, 2 DLTs/3 patients, or 3 DLTs/3 patients), the playbook provides the model estimated MTD for the next cohort, the posterior variance, and a stop/continue dosing recommendation.

While the SRC will consider the model estimated MTD in Part A, the SRC alone will be responsible for making the recommendations for the dose-escalation, including the assignment of a dose-level not recommended by the playbook.

The playbook for each subsequent cohort will be provided by AstraZeneca or INC once the SRC has agreed upon the number of DLTs that occurred in the previous cohort INC will generate back-up copy of the playbook in case it may be needed for the SRC.

### 11.1.3. Confirmation of the Presumed Recommended Dose

Once the MTDs for each of the 2 agents in combination with MEDI4736 have been identified or the maximum doses of each of the 2 agents in combination with MEDI4736 have been reached, the SRC may decide to enrol an additional cohort of at least 6 evaluable patients per treatment arm to confirm the presumed recommended dose for each of the 2 agents in combination with MEDI4736 to be further explored in the dose-expansion Part B.

Once all patients have completed Part A, the final estimates of the proportion of DLTs for each tested dose-level of the 2 combination will be summarized.

## Statistical Analysis Plan

The subsequent sections of Section 11 describe the analyses that will be conducted on the safety variables common to Part A and Part B.

### 11.2. TREATMENT EXPOSURE AND DURATION

Exposure is defined as the total amount (in mg) of a study drug component (AZD9150, AZD5069, and MEDI4736) that is received by a patient.

Total treatment duration will be calculated separately for each of the components of study medication. Because the pharmacokinetic profiles of AZ9150, AZD5069, and MEDI4736 differ, the total treatment duration is defined differently for each component of study medication:

For AZD9150:

Total treatment duration (days) = (Date of last dose - date of first dose in Cycle 1) + 7).

For AZD5069:

Total treatment duration (days) = (Date of last dose - date of first dose in Cycle 1) + 1).

For MEDI4736:

Total treatment duration (days) = (Date of last dose - date of first dose in Cycle 1) + 28).

For treme in arm A4:

Total treatment duration (days) = (Date of last dose - date of first dose in Cycle 1) + 28).

Actual treatment duration (days) will be calculated as the total duration of exposure, excluding periods of dose interruption (AZD5069) and planned “no dose” periods for intermittent dosing (AZD9150 and MEDI4736). For AZD5069, periods of dose interruption will be defined as days within the treatment period on which the patient took no tablets of AZD5069. For AZD9150, each planned “no dose” period will be counted as 7 days. For MEDI4736 or treme, each planned “no dose” period will be counted as 28 days.

Duration of therapy (months) is the actual treatment duration for the dose to which the patient was originally assigned or randomized. Duration of therapy will be calculated only for Part B.

The relative dose intensity is the percentage of the actual dose intensity delivered (mg/kg based on ideal body weight) divided by the intended dose intensity (mg/kg based on ideal body weight) through to treatment discontinuation multiplied by 100. The duration of the intended cumulative intended dose is defined as the time up to the earlier of progression (or a censoring event) or the actual last day of dosing.

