7.2.3 Administration of MEDI4736

MEDI4736 will be administered on an mg/kg (with the exception of Arm B8) basis Q4W via a 1-hour IV infusion.

MEDI4736: Arms (A1 to A7, B1 to B4, B7): Patients will receive MEDI4736 starting Day 1 of Cycle 1 administered as a 20 mg/kg infusion over 1 hour Q4W in a 28-day cycle. In addition to the above arms, patients in monotherapy arms (B5 and B6) who develop confirmed disease progression may have MEDI4736 added, at the discretion of the Investigator and after notifying the Medical Monitor. MEDI4736 will be added to the dosing schedule beginning on Day 1 of the following treatment cycle. Thereafter, all study treatment will follow the same schedule as for a patient on a combination therapy arm.

For patients in B8, a 1.5 g flat dose will be administered via infusion starting Day 1 of Cycle 1 over 1 hour Q4W in a 28-day cycle. If body weight decreases to less than 30 kg, weight-based dosing (20 mg/kg Q4W) will be implemented.

Patients will receive MEDI4736 on Day 1 of each treatment cycle, starting with Cycle 1; doses have a ± 2 day dosing window. Weight obtained on Day 1 of each cycle will be used to calculate the weight-related dose of MEDI4736 for each cycle.

Patients should be observed after administration of MEDI4736 for a minimum of 2 hours for the appearance of any acute drug reactions. In the event of an acute reaction, in order to help understand the potential drug relatedness of such a reaction, a blood sample should be drawn

during the event for possible additional ADA testing. Serum tryptase or other blood or urine testing relevant to the diagnosis of anaphylaxis may be obtained at the discretion of the Investigator.

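### SAP 11.2: AZD9150 duration is 7 days short in the every-2-week arms, and the actual-duration rule, read literally, cancels an on-schedule course

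*SAP*

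**What the plan says.** SAP 11.2 defines a total duration for each drug. For AZD9150 it is "Total treatment duration (days) = (Date of last dose - date of first dose in Cycle 1) + 7". MEDI4736 and tremelimumab each have "Total treatment duration (days) = (Date of last dose - date of first dose in Cycle 1) + 28", and AZD5069 has the same form with +1. No arm is excepted.

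Actual duration is derived from total duration: "Actual treatment duration (days) will be calculated as the total duration of exposure, excluding periods of dose interruption (AZD5069) and planned" no-dose periods, which the SAP ties to the intermittent dosing of AZD9150 and MEDI4736. The charges are fixed: "For AZD9150, each planned “no dose” period will be counted as 7 days" and "For MEDI4736 or treme, each planned “no dose” period will be counted as 28 days". Part B then uses the result: "Duration of therapy (months) is the actual treatment duration for the dose to which the patient was originally assigned or randomized".

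Relative dose intensity is defined once, with no drug named: "percentage of the actual dose intensity delivered (mg/kg based on ideal body weight) divided by the intended dose intensity (mg/kg based on ideal body weight".

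The dosing bases differ. Protocol 7.2.1 puts Arm B8 and one cohort of Arm A4 on AZD9150 every 2 weeks. SAP 3.7 uses ideal body weight for AZD9150 only, and not in B8. Protocol 7.2.3 says of MEDI4736: "Weight obtained on Day 1 of each cycle will be used to calculate the weight-related dose of MEDI4736 for each cycle"; in B8 it is a flat 1.5 g. AZD5069 is a fixed mg dose. Protocol 8.10 requires relative dose intensity for all three drugs, states no weight basis, and defines total exposure with +1 throughout. SAP section 13 lists only changes to analysis sets.

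**The concern.** The offset after the last dose equals one dosing interval for daily AZD5069 (+1), weekly AZD9150 (+7) and 4-weekly MEDI4736 and tremelimumab (+28). The every-2-week AZD9150 arms are the only ones where it does not.

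The actual-duration rule credits one interval per dose and then removes planned no-dose periods of exactly one interval each. If those periods are the gaps in the schedule, the two steps cancel. The interruption clause names AZD5069 only, so on a literal reading unplanned delays of infused drugs are never removed.

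What is at stake is whether total duration, actual duration and Part B duration of therapy describe how long patients were treated in each arm.

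**Working it through.** The plan states no exposure figure to reproduce. The check applies its formulas to on-schedule dose dates, with a 28-day cycle (SAP 6.2) and counting from the first Cycle 1 dose.

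**Convention where it fits.** Weekly AZD9150, 4 doses per cycle: (4c − 1) × 7 + 7 = 28c, giving 28, 84 and 168 days for 1, 3 and 6 cycles. MEDI4736, n doses: 28(n − 1) + 28 = 28n. Both equal the calendar length of the cycles completed.

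**AZD9150 every 2 weeks**, 2 doses per cycle: (2c − 1) × 14 + 7 = 28c − 7.

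| Cycles | Doses | With +7 | With +14 | Shortfall |
|---|---|---|---|---|
| 1 | 2 | 21 | 28 | 7 days (25%) |
| 3 | 6 | 77 | 84 | 7 days (8.3%) |
| 6 | 12 | 161 | 168 | 7 days (4.2%) |
| 12 | 24 | 329 | 336 | 7 days (2.1%) |

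**Actual duration, no-dose periods read as scheduled gaps.** There are n − 1 gaps between doses, or n if the gap after the last dose also counts.

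| Drug, on schedule | Total | Minus n − 1 gaps | Minus n gaps |
|---|---|---|---|
| MEDI4736, 6 doses | 168 | 168 − 140 = 28 | 168 − 168 = 0 |
| MEDI4736, 12 doses | 336 | 336 − 308 = 28 | 336 − 336 = 0 |
| AZD9150 weekly, 24 doses | 168 | 168 − 161 = 7 | 168 − 168 = 0 |
| AZD9150 every 2 weeks, 12 doses | 161 | 161 − 77 = 84 | 161 − 84 = 77 |

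A delay lengthens the result. With the sixth MEDI4736 dose 14 days late, total is 154 + 28 = 182, and actual is 182 − 140 = 42 or 182 − 168 = 14. The patient with the delay scores higher than the one without.

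**Actual duration, no-dose periods read as scheduled doses not given.** MEDI4736 with 6 of 6 doses given: 168. With 5 of 6 given and one missed mid-course: 168 − 28 = 140. This is 28 × doses given, a usable figure.

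**Relative dose intensity for MEDI4736, every dose given in full.** The weights are assumptions for illustration: ideal 70 kg, measured 90 or 60 kg.
- Delivered mg per kg ideal weight against a nominal 20 mg/kg: (90 × 20 / 70) / 20 = 129%; (60 × 20 / 70) / 20 = 86%.
- Delivered and intended mg both divided by 70: (1800 / 70) / (1800 / 70) = 100%.

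**The case against.** The strongest defence concerns actual duration. A 4-week gap contains 27 dose-free days and a weekly gap 6, yet the SAP charges 28 and 7. Those constants fit one dosing interval in which no dose was given, and that reading parallels the AZD5069 rule, which removes days without tablets. AZD9150 also has genuine dose-free weeks: alternate weeks in the every-2-week arms, and Days 8 and 22 for some dose-reduced patients (Protocol Table 5 footnotes). This shows that a workable intention is plausible. It does not rescue the text, which speaks of planned periods in intermittent dosing; an omitted dose is not a planned no-dose period. The fair criticism is that the term is undefined and that its literal reading destroys the variable. The 28-or-0 result holds for on-schedule patients only.

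On the 7-day offset, the SAP's stated reason for using different formulas is the drugs' pharmacokinetic profiles, not their dosing intervals. The interval convention is therefore inferred, though it fits every other regimen.

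Three stronger readings are tempting but unsupported:
- **MEDI4736 dose intensity is necessarily distorted.** Ideal weight appears in both numerator and denominator, so it can cancel. The 129% and 86% arise only if the intended intensity is taken as the nominal mg/kg, which the SAP does not say.
- **Exposure is the denominator for safety and efficacy.** Percentages use the number of patients (SAP 6.1), adverse event tables count patients (11.3), and ORR uses the Efficacy set (8.2.2).
- **B8 cannot be compared with B7.** A constant 7 days does not do that. MEDI4736 total duration uses +28 in both arms, and doses received, mg exposure, time on study and percent intended dose are also reported.

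**Conclusion.** The point stands in two parts. Total AZD9150 duration in B8 and the every-2-week A4 cohort is 7 days short relative to the weekly arms at any length of treatment: 25% at one cycle, 4.2% at six. This assumes on-schedule dosing and that the offset is meant to be one dosing interval.

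Actual duration, with planned no-dose periods read as the scheduled gaps, does not measure treatment length for MEDI4736, tremelimumab or weekly AZD9150, and it leaves unplanned delays of infused drugs in. Part B duration of therapy inherits the problem. A reading that the text does not state gives sensible values, so the defect lies in the written rule; the documents do not show that the tables were programmed that way.

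The ideal-weight basis for relative dose intensity is a secondary clarification. It suits only AZD9150 outside B8, and whether it changes any number depends on how the intended intensity is expressed.

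The effect is confined to descriptive exposure summaries.

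**What to change.** In SAP 11.2:
- Make the offset the arm's own dosing interval: +7 for weekly, +14 for every 2 weeks, +28 for every 4 weeks.
- Define actual duration as total duration minus scheduled doses not given and unplanned delays or interruptions, for infused drugs as well as AZD5069. Drop the planned no-dose wording, or define it so that ordinary gaps between doses are not subtracted.
- State relative dose intensity as mg given over mg planned, on each drug's own dosing basis: measured weight for MEDI4736 outside B8, flat mg for B8 and AZD5069, and the protocol's dosing weight for AZD9150 elsewhere.

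In SAP section 13, list the duration formulas as a change from the protocol, because Protocol 8.10 uses +1 for every drug.

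The cost is SAP wording and an update to the exposure programs. These are analysis definitions only; no dosing rule changes.
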